5.2 Eligibility and Exclusion Criteria

Study eligibility is determined by a set of specific inclusion and exclusion criteria. Individuals must meet all eligibility criteria. This section defines the criteria, method for determination, and the specific forms needed to document eligibility.

Our specific inclusion criteria include:

- Type II diabetes mellitus with HbA1c $\geq 7.5\%$ using food bank point-of-care testing
- Food pantry client (defined as any individual engaging with a food bank or partner agency for food assistance, regardless if is their first visit or not, or if they are requesting direct food assistance, SNAP enrollment assistance, or general information on any food resources or programming)
- Reliable mode of contact (either phone or address) where they can be reached
- English or Spanish verbal fluency
- 18 years of age or older
- Intent to remain in the study area for at least the next 12 months
- Willingness to participate in intervention (including picking up bi-monthly food boxes and participating in diabetes education activities)

Exclusion criteria include:

- Type 1 diabetes
- Pregnant or less than 6 weeks post-partum*
- Cognitively impaired: dementia, mental illness, or active substance abuse severe enough to make client incapable of providing informed consent and could interfere with administration of the survey or participation in the intervention**
- Household member already enrolled in the study***

* Study participants who become pregnant after enrollment may remain in the study and participate in all study activities in their assigned group (intervention or control). Study staff will emphasize with any pregnant study participant the importance of staying connected with their healthcare providers (to receive regular pre-natal care and any pregnancy-specific diabetes self-management education and support).

** Refer to **Appendix AS** “Cognitive Impairment Assessment Tool” to assess cognitive impairment during participant enrollment; this form and process need only be used on clients where study staff suspect cognitive impairment.

*** Other household members with diabetes can share the food box, participate in the education, and have their HbA1c checked, but should not be enrolled in the study.

5.2.1 Prompts for speaking with ineligible clients

During the screening and enrollment process, it is likely that food bank staff will interact with clients who want to enroll in the project, but who do not qualify based on the study eligibility requirements. For example: a client who has an HbA1c result of 7.4%, or is planning on moving away in 11 months, or does not speak English or Spanish fluently would be excluded from study participation. The following prompts are to provide guidance to project staff to communicate this information to the client, with the goals of ensuring that the client understands and has a positive pantry experience.

- Emphasize that because this is a research study, enrollment requirements are very clear and are not flexible (potentially a difference from other pantry programs); adhering to the protocol will allow the researchers to learn what best helps participant with diabetes
- Provide information about other pantry or community resources for which the participant may be eligible
- If the client may become eligible in the future (e.g., has an increased HbA1c, or exits out of the 6-week post-partum period), then encourage the participant to return in the future for additional screening and assessment of eligibility
 - It may be important to stress that the enrollment period will have an end date, and there is no guarantee that enrollment will be possible at a later date
 - For clients with an elevated HbA1c level that is not high enough to qualify for the study (e.g., an HbA1c 6.5% - 7.4%), it is **essential** to provide the client with positive feedback

that they are doing a tremendous job in managing their diabetes well and that they should continue working hard to keep their HbA1c level under 7.5% (we do not want clients “sabotaging” their diabetes self-management in order to enter the study)

- Remind clients that the study is helping the food bank to learn more about community based interventions that help people living with diabetes; it is likely that the food bank will offer additional diabetes programming after the study ends that will have much less strict enrollment requirements

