3.1.1 Testing for diabetes and diabetes control among food pantry clients

In order to identify food bank clients who may be eligible for study participation, food bank project staff will offer free diabetes screening events at food pantry sites during the recruitment phase of the study. Diabetes screening will be provided at no cost for any food pantry client who is interested in and verbally consents to the screening, and is over 18 years of age. Food bank staff will conduct all screening activities, emphasizing with food pantry clients that screening tests are **not** diagnostic and that clients should speak directly with their health care providers for diabetes risk assessment, evaluation, and treatment.

For food pantry clients with no reported history of diabetes, or no known history of diabetes, diabetes screening will first include a random blood glucose (RBG) test using a Point-of-Care (POC) glucometer and a finger stick capillary whole blood sample. Clients who have an elevated RBG screening result (defined as ≥ 160 mg/dL in non-fasting individuals and ≥ 140 mg/dL in fasting individuals) will also receive a screening glycosylated hemoglobin A1C (HbA1c) test using a POC device.

All screening tests will be performed by trained study or food bank staff, or by trained food bank volunteers. All study staff and volunteers with human subjects contact must have appropriate CITI certification and quality and safety training. Screening staff will complete the information on the Screening Log (Appendix B) for **every** food pantry client who receives a blood glucose and/or HbA1c test. If uncertain, staff can ask the client for specific information in order mark the appropriate boxes under “age”, “gender”, and “race/ethnicity” (otherwise, staff can complete that information based on their assessment of the client.

For food pantry clients who self-report a history of diabetes, screening will consist of a POC HbA1c test using a finger stick capillary whole blood sample performed by trained personnel.

All clients who participate in screening will receive written results of their screening tests (see Client Screening Results Form in **Appendix J**), along with basic information about their results and local community health care resources.

Additionally, any food pantry client who receives an HbA1c test will receive an educational handout (see **Appendix AK**) with information about the category in which their result falls:

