All food pantry clients participating in diabetes screening events will be informed by staff that screening results are **NOT** diagnostic. Staff will direct clients to contact their primary medical provider or a community health center to address all personal medical and health questions, and for further screening, evaluation, and treatment as needed. Staff will provide food pantry clients with contact information for local community health care organizations as part of the screening process.

Each food bank site is only expected to conduct regular screening activities until that site reaches its target number of enrolled participants (240 per site). Once study recruitment and enrollment has ended, each site will only be required to continue testing and monitoring enrolled participants per the study timeline. Sites can continue to conduct general screening activities with pantry clients if they have the time, resources, and capacity. However, no new screening information should be tracked in ACCESS after enrollment has closed, and pantry clients screened after the enrollment has closed may not participate in study activities or interventions. Sites can develop their own protocols (e.g.,

referral processes for clients needing care, educational programming, food resources) for managing pantry clients and screening activities beyond what is required for this trial.

When an adult food pantry client provides verbal consent and agrees to participate in a diabetes screening test, we will use the following flow chart to identify what screening tests and procedures are used:

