	 Fasting  Non-fasting		 YES	 18-40  41-60  61+	 Female  Male	 White  Black  Latino  Other	 ENROLLED NOT ENROLLED DUE TO:  Doesn't speak Eng or Sp  HH member enrolled  Type I diabetes  Pregnant/<6 wks postpartum  Not pantry client  Cognit. impaired  Not in area for next 12 mos.  Declined: _____  No reliable contact info
	 Fasting  Non-fasting		 YES	 18-40  41-60  61+	 Female  Male	 White  Black  Latino  Other	 ENROLLED NOT ENROLLED DUE TO:  Doesn't speak Eng or Sp  HH member enrolled  Type I diabetes  Pregnant/<6 wks postpartum  Not pantry client  Cognit. impaired  Not in area for next 12 mos.  Declined: _____  No reliable contact info

1. Fasting is more than 8 hours from last intake.
2. Perform HbA1c if: history of diabetes or gestational diabetes, fasting blood sugar 140 or higher, or non-fasting blood sugar 160 or higher.
3. Do not check blood sugar or HbA1c on any person younger than 18 years of age.

[figure not shown]

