Appendix J – Screening Results Form [English]

Thank you for having your blood sugar and/or hemoglobin A1c (A1C) checked here today. Your A1C tells you what your average blood sugar was for the last three months. If your A1C is high, you may have diabetes. For people who already have diabetes, a common goal is to have an A1C close to 7%.

Your blood sugar is: _____ mg/dL (normal is 70 – 160)

Your A1C is: _____ %

- This is normal (A1C 5.6% or less).
- This is a little high (A1C 5.7% - 6.4%). You may have pre-diabetes. We suggest you see your doctor to find out for sure whether you have pre-diabetes.
- This is high (A1C 6.5% or higher). You may have diabetes. We suggest you see your doctor to find out for sure whether you have diabetes.

Your A1C test result is not a diagnosis of pre-diabetes or diabetes. Only a doctor can tell you whether you have pre-diabetes or diabetes, or if your diabetes is well-controlled. Please see the back of this form for information about community health care centers and additional food resources.

(Site Specific Information)

Food Resources

- Food Bank:
- SNAP:
- Special Nutrition Program for Women, Infants, and Children (WIC):

Community Health Centers & Programs

- Clinic 1
- Clinic 2
- Clinic 3
- Clinic 4
- Local DPP
- Local DSME Program

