Appendix K – Screening Results Form [Spanish]

Gracias por haberse verificado los niveles de azúcar en la sangre y de hemoglobina A1c (A1C) hoy. Su A1C le dice su promedio del nivel de azúcar durante los últimos tres meses. Si su A1C es alto, es posible que usted tenga diabetes. Para las personas que ya tienen diabetes, un objetivo común es tener un A1C cerca de 7%.

El nivel de azúcar en su sangre es: _____ mg/dL (normal es 70 – 160)

Su A1C es: _____ %

- Esto es normal (A1C 5.6% o menos).
- Esto es un poco alto (A1C 5.7% - 6.4%). Es posible que usted tenga pre-diabetes. Le sugerimos que visite su doctor para averiguar si usted tiene pre-diabetes.
- Esto es alto (A1C 6.5% o más alto). Usted puede tener diabetes. Le sugerimos que visite su doctor para averiguar si usted tiene diabetes.

Su A1C resultado de la prueba no es un diagnóstico de pre-diabetes o diabetes. Solo un doctor le puede decir si tiene pre-diabetes o diabetes, o si su diabetes está bien controlada. Por favor consulte la parte atrás de esta forma para información sobre centros comunitarios de salud y más recursos para comida.

(Site Specific Information)

Recursos de Comida

- Banco de alimentos o despensa: Food Bank:
- SNAP (estampillas para comida):
- Programa de Nutrición Suplementar para Mujeres, Bebés, y Niños (WIC):

Centros y Programas de Salud en la Comunidad

- Clinic 1
- Clinic 2
- Clinic 3
- Clinic 4
- Local DPP
- Local DSME Program

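### Section 5.2.1 has staff praise ineligible clients at HbA1c of, for example, 6.5%–7.4% for managing their diabetes, with no condition on prior diagnosis; for a never-diagnosed client this is inconsistent with Appendices J and K

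*Combined protocol and SAP*

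**What the plan says.** Section 5.2.1 guides staff in talking to people who would like to join but are not eligible. One item begins "For clients with an elevated HbA1c level that is not high enough to qualify for the study" and gives 6.5%–7.4% as the example range. For this group it calls positive feedback essential: the client is to hear that "they are doing a tremendous job in managing their diabetes well" and should keep working to stay under 7.5%. The stated reason is to avoid clients letting their control slip in order to get in.

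Section 3.1.1 describes a separate route that starts "For food pantry clients with no reported history of diabetes, or no known history of diabetes". These clients have a random glucose test first, and an HbA1c test if the glucose is elevated. Section 3.1.3 repeats the thresholds. Footnote 2 of the Screening Log (Appendix B) reads "Perform HbA1c if: history of diabetes or gestational diabetes, fasting blood sugar 140 or higher, or non-fasting blood sugar 160 or higher".

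Under Section 3.1.1 everyone screened gets a written results form. In Appendix J the box for this range reads "This is high (A1C 6.5% or higher). You may have diabetes" and goes on to suggest seeing a doctor. The form adds that the result is not a diagnosis and that "Only a doctor can tell you whether you have pre-diabetes or diabetes, or if your diabetes is well-controlled". Appendix K says the same in Spanish: "Solo un doctor le puede decir si tiene pre-diabetes o diabetes". Section 5.1 has staff tell all screened clients that results are not diagnostic, and adds "Staff will direct clients to contact their primary medical provider or a community health center".

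**The concern.** The prompt in Section 5.2.1 selects its audience by HbA1c value and not by history. For a client with known diabetes the message is ordinary encouragement. For someone whose first HbA1c result has just come back in the diabetes range, it assumes a diagnosis nobody has made and calls the result a success. The form handed over at the same event calls that result high and sends the client to a doctor.

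What is at stake is communication with people who will not be participants: a conflicting spoken message and some risk of false reassurance. Trained volunteers may do the screening (Sections 3.1.1 and 14.3), and the manual plans for clients who cannot read its consent materials (Section 5.3.2). For some clients the spoken words may therefore be what they take away.

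**Working it through.** No sample size, power or error rate is involved, so the check sets the texts side by side.

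1. **Who the prompt covers.** Ineligible clients who want to enroll and have a raised HbA1c below the 7.5% entry cut-off. The example band is 6.5%–7.4%, that is 7.4 − 6.5 = 0.9 percentage points wide. Section 5.2.1 states no condition on history.

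2. **Can a never-diagnosed client have a result in that band?** Yes. Sections 3.1.1 and 3.1.3 give such clients an HbA1c test at a glucose of 140 mg/dL or more fasting, or 160 mg/dL or more non-fasting. Appendix B adds clients whose only history is gestational.

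3. **Can that client be a would-be enrollee?** Yes. Section 3.1.1 moves clients to eligibility assessment on an HbA1c of 7.5% or more. Section 5.2 requires type 2 diabetes with that value on the food bank's own test. Neither asks for an earlier diagnosis, so a client first identified at screening may want to join and miss the cut-off.

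4. **Does the same client get the form?** Yes. Every screened client does, and its box for 6.5% and above contains the whole 6.5%–7.4% band.

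5. **The two messages for that client:**

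| Element | Section 5.2.1 prompt | Appendix J/K |
|---|---|---|
| Diagnosis | Presumed | Possible; the test is not a diagnosis |
| Level | Presented as a success | High |
| Action | Carry on; stay under 7.5% | See a doctor to find out |
| Control | Good | For a doctor to judge |

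The first three rows show the conflict for a never-diagnosed client. The fourth applies to diagnosed clients as well, so the point does not rest on it.

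6. **Is the praise reasonable for a client with known diabetes?** Yes. Appendix J gives a common goal for such people of about 7%. The band runs from 7.0 − 6.5 = 0.5 points below that to 7.4 − 7.0 = 0.4 points above it.

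7. **What else the never-diagnosed client receives.** Besides the form and the spoken caution, staff explain the result (Section 7.3.1, step 28). Non-enrolled clients get a resource handout, and those without a primary care provider get a faxed referral (Section 3.2.1). The draft clinic agreement (Appendix O) provides for referral from HbA1c 5.7% for clients without a provider, follow-up appointments for clients already in care at the clinic, and encouragement to book with an existing provider where direct referrals are not taken. Section 5.2.1 cancels none of this.

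8. **What could not be checked.** The screening flow chart announced in Section 5.1 is a figure that was not available. Section 5.1 describes it as determining the tests and procedures used, and does not say that it governs the wording in Section 5.2.1. A split by history there cannot be ruled out.

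**The case against.** The strongest reply is that the authors plainly had known diabetes in mind. The prompt speaks of managing, of continuing, and of self-management, none of which suits a person who has just learned of a possible problem. These are prompts, used by staff who have already asked about a prior diagnosis (Section 7.2.1, step 3; Section 7.3.1, step 4). This is probably the right account of intent. It does not supply the missing condition: followed literally, the text covers the never-diagnosed client. That is a reason to write the intent in.

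A second reply is that the correct message is already mandatory. This stands, and it keeps the risk small.

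A third is that the praise serves to discourage clients from letting control slip. This also stands, and the fix has to keep that advice for everyone in the band. Naming 7.5% to clients discloses nothing new, since Section 5.2.1 already has staff mention it.

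A reader might also infer more than the documents support:

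- That never-diagnosed clients are left without a route to care. The referral and see-a-doctor provisions listed above say otherwise.
- That staff may not praise diagnosed clients either, because Appendix J leaves the judgment of control to a doctor. That sentence does apply to everyone, but for a diagnosed client no diagnosis is presumed and the encouragement is reasonable.
- That the trial is compromised. The clients concerned are ineligible and are not randomized.

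**Conclusion.** The point holds as an inconsistency of wording with a small safety aspect. Read literally, Section 5.2.1 gives a never-diagnosed client in the 6.5%–7.4% range praise that presumes a diagnosis and is at odds with Appendices J and K. Its reach is limited to ineligible clients who want to enroll, fall in that range, and have no diabetes diagnosis other than gestational. The documents give no count of them, and none is assumed here. Randomization, endpoints and analysis are unaffected. The conclusion assumes that staff follow the written text and that the flow chart in Section 5.1 does not already separate clients by history for this prompt. It is a cheap improvement to consider and does not identify a flaw in the trial.

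**What to change.** In Section 5.2.1, limit the praise to clients who report a prior diabetes diagnosis (other than gestational only), and leave its wording unchanged for them. For others in the band, staff repeat the Appendix J/K message (high, may have diabetes, not a diagnosis, see a doctor) and say that they cannot enroll at this level. Keep for all clients the advice to work to keep HbA1c from rising.

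The split uses the history question staff already ask. A client with past gestational diabetes might answer yes to it, so staff should confirm whether the diabetes was only during pregnancy. Appendix AI already lists gestational diabetes separately from types 1 and 2.

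The cost is one added clause and a brief training note covering the message for other clients and the gestational check. No new test, form or data field is needed, and Appendices J and K stay as they are.

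Relabelling the controlled-diabetes category in the staff text of Sections 3.1.1 and 14.1 and Appendix AK is not recommended. Appendix AK would still assign a handout titled for type 2 diabetes to the whole band, so the relabel would not remove the presumed diagnosis.

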5.3 Informed Consent

Informed consent is a process in which an eligible individual is informed of all aspects of the research that are relevant to his or her decision and is then given the chance to choose whether or not to participate without any consequence to usual care.

US regulations 21 CFR 50 and 45 CFR 46 require that informed consent be documented by the use of an informed consent form approved by the responsible institutional review board (IRB) and signed and dated by the participant and research staff at the time of consent. Detailed instructions for obtaining informed consent are listed below and a quick guide to the informed consent process (Western Institutional Review Board, except from “A Guide for Researchers”) can be found in **Appendix T**. In addition, a copy of this study’s informed consent form can be found in **Appendix AE**.

The informed consent form and process has been approved by the Western Institutional Review Board.

5.3.1 The Informed Consent process for participants with adequate literacy

- **Review eligibility:** Before initiating the informed consent process, be sure to review the eligibility of the potential participant and make sure this information is accurately recorded on the screening and enrollment checklists.
- **Verbally explain the study and research activities:** Using the informed consent form as a guide, verbally go through each section (section headings are in bold) of the form with the potential participant, speaking clearly and allowing the potential participant to ask questions. The consent form and consent process must be completed in the potential participant’s preferred language (either English or Spanish).
- **Provide the written consent:** When the verbal consent process is complete, provide the participant with the written form for them to read. The participant must be given sufficient time to read and consider what is required of them, the risks, benefits, and alternatives of participating before providing their consent.
- **Assess client comprehension:** In addition to fielding questions from the potential participant, the person obtaining the consent must assess the food bank client’s comprehension by using the teach-back method whereby the person obtaining consent asks open-ended and non-directive questions that require the potential participant to explain in his or her own words the

basic study procedures. Research staff should make sure the potential participant can describe why the research is happening, what is being asked of him or her, and the risks and/or benefits to taking part in the study. Some sample questions include:

- If someone in your family asked you what this study was about, what would you tell them?
 - How often might you need to pick up food boxes as part of this study?
 - Where will you be picking up your food boxes during the study?
 - If you had a question or problem during the study, who could you contact?
 - What else might you receive for participating in this study?
 - How many diabetes classes might you be expected to participate in during the study?
- **Obtain consent:** Once all questions are answered by both parties and the individual has agreed to participate in the study, the participant should sign and date the consent form where indicated. The research staff member who performed the consent procedures should sign and date the same consent form. The participant and research staff should also sign a second consent form for the participant to keep as a copy for their records.
 - **Store and track signed forms:** Once the consent is complete, the original form should be stored in an informed consent binder at the individual site. This material is sensitive and access should be restricted to trained FAITH-DM study personnel only (**see section 17.4**). Documentation that the consent was or was not completed should be noted on the appropriate tracking forms in the MS Access database.

